Overview of the study design. Prior to the waitlist-controlled trial, we will conduct a qualitative, user-centered design process with up to 10 pairs of older adults with symptoms of SCD/MCI and ELLs to iteratively refine the training protocols and the materials that will support productive, engaging conversations. We then will conduct a mixed-methods pilot randomized trial with a waitlist control group in which 44 pairs of older adults with symptoms of SCD/MCI and ELLs will be recruited from a variety of sources. Pairs will participate in webcam conversations supported by research staff for 8 weeks, using materials designed to promote positive and effective conversation sessions. Data will be collected from older adults with symptoms of SCD/MCI and ELLs via observations of videoconference sessions, qualitative semi-structured interviews, and quantitative surveys at baseline and the 8-week follow-up. The primary goal of the randomized pilot study will be to evaluate our capacity to recruit pairs, implement the intervention, and retain participants with symptoms of SCD/MCI in sufficient numbers for a subsequent trial evaluating the intervention's impact on participants' psychological well-being, mood, and cognitive functioning. We also will use mixed methods to evaluate the communication process between older adults with symptoms of SCD/MCI and ELLs including factors that contribute to satisfaction of both parties, engagement in sessions, contributors to dissatisfaction or dropout, and perceptions among older adults with symptoms of SCD/MCI of being appreciated and effective. Finally, using data from the waitlist-controlled trial, we will estimate variances for key outcome variables for planning the subsequent clinical trial, and we will conduct exploratory analyses of intervention-control differences in participants' perceptions of their wellbeing, mood, and cognitive functioning.

Sequence of the investigation. Months 1-6 will be devoted to developing protocols and materials for screening/surveys, recruitment, training, and supervision of sessions. In Months 7-11 we will conduct a user-centered design process (Aim 1) and refine protocols and materials in preparation for the trial. Months 12-17 will be devoted to enrolling 44 pairs of older adults with symptoms of SCD/MCI and their ELL partners for the pilot trial. Older adults' cognitive functioning,

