Aim 2-3 waitlist controlled trial. While our primary scientific goal is not to evaluate intervention-control differences in outcomes, we will include a waitlist control group in order to get an unbiased estimate of recruitment rates for that subsequent randomized clinical trial. We will generate a randomization sequence and randomization envelopes to assign 44 older adults to the intervention or waitlist control group (1:1 ratio). Randomization will be conducted after older adults with symptoms of SCD/MCI complete their baseline survey. Older adults with symptoms of SCD/MCI assigned to the intervention will be matched with an ELL for 8 weeks of hourly SPEAK! sessions with orientation and materials refined as part of Aim 1. Older adults with symptoms of SCD/MCI assigned to the waitlist control will be matched with an ELL after completing their 8-week follow-up survey, at which time the pair will complete the 8-week intervention.

Quantitative measures for Aims 2-3. Older adult with symptoms of SCD/MCI surveys. Sociodemographic characteristics of older adults with symptoms of SCD/MCI will be measured using standard items to evaluate the generalizability of the study findings and possible moderators of intervention effects. General health status will be measured at baseline using standardized items to identify common chronic diseases. At baseline and follow-up, older adults with symptoms of SCD/MCI will complete the Psychological Well-Being Scale (PWB), a validated measure shown to be sensitive to intervention effects and with subscales measuring respondents’ sense of autonomy, environmental mastery, personal growth, positive relations with others, life purpose, and self-acceptance. The PWB will be supplemented with measures

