Primary outcome and sample size for the pilot trial. The pilot trial (Aims 2-3) has been designed to be consistent with the goals of pilot studies articulated by Thabane et al., i.e.: to assess key processes (rates of recruitment, retention, and engagement); determine resources needed for a definitive trial (e.g., staff time required for recruitment and intervention delivery), and possible issues related to patient safety, dose-response, and variation of treatment effects. We expect that the outcomes for a larger, statistically-powered trial will be the Psychological Well-Being Scale (PWB) with secondary outcomes being measures of cognitive functioning and mood. The current trial is not intended to estimate those effect sizes, but rather to optimize the intervention and ensure that we have the capacity to reach the subsequent trial’s recruitment goals given expected timeline and resources. For that larger trial, we estimate we would need resources to recruit, retain, and implement the intervention with approximately 262 pairs recruited over 36 months. A target sample of this size would be sufficient to detect a small/medium impact on Psychological Wellbeing scores (PWB; Cohen’s $d=0.45$) with 0.90 power, a 0.05 probability level, and assuming a 20% dropout rate. To assure that we have the capacity to enroll at that same rate, we will recruit 44 pairs in the waitlist trial for Aims 2-3 over 6 months. According to the Poisson distribution, if our observed recruitment over 6 months falls below 35 pairs, that would indicate that we would be unlikely to be able to recruit our target sample of 262 in the subsequent trial over 36 months ($P<.10$). We will conduct monthly reviews of our observed versus expected recruitment rate, and should recruitment fall more than 10% below expectation in the first two months, we will seek out additional sources of older adults with symptoms of SCD/MCI as described above.

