Additional analysis for Aims 2-3. Older adults with symptoms of SCD/MCI will be asked to consent to a brief screening survey, and initial analyses will focus on the sociodemographic, health, and mental health characteristics of potential participants who do versus do not enroll, and reasons for non-participation. Recruitment rates will be tracked overall as well as by gender, age, race/ethnicity, and educational attainment. Among enrollees, we will calculate descriptive statistics of the proportion of older adults with symptoms of SCD/MCI who choose to discontinue participation, as well as baseline predictors of dropout and session completion, with a particular emphasis on baseline measures of cognitive functioning, and psychological indicators such as PWB and depressive symptoms. While these will be quantitative analyses, results will not include statistical inference (i.e., “p-values”). **For Aim 3.** We will examine correlations between measures of (a) intervention satisfaction and the number of missed sessions, and (b) baseline measures of characteristics of older adults with symptoms of SCD/MCI including measures of cognitive functioning and PWB. Examination of intervention/control differences in PWB will be purely exploratory and used to generate hypotheses and strategies for modifying the intervention to make it more impactful. Change scores for continuous outcomes (e.g., PWB) will be computed, and differences across randomization groups will be compared using the Wilcoxon rank sum test.

In a purely exploratory mode, we will examine differences in outcomes between intervention and control groups, controlling for any baseline differences in group characteristics. Older adults who drop out of the program or who complete less than the expected number of sessions but complete outcome surveys will be included in outcome analyses. We also will conduct 'completer' analyses including only intervention-group older adults who complete 8 out of the 12 planned sessions (or the equivalent out of 8 planned sessions). Whenever possible, we will create graphical displays comparing pre-post changes in outcomes across groups to make the findings as interpretable as possible for various audiences.

IV. Potential Risks, Minimizing Risks, and Potential Benefits

Protection of Human Subjects

Human Subjects Involvement and Characteristics

1. Risk to Subjects

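### No interval is planned for dropout, and the exploratory change-score comparison is specified only as a Wilcoxon test with no effect estimate or interval

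*Combined protocol and SAP*

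**What the plan says.** Section II, Overview of the study design, includes in the pilot's primary goal the capacity to "retain participants with symptoms of SCD/MCI in sufficient numbers for a subsequent trial". Section III, Primary outcome and sample size for the pilot trial, lists retention and engagement with recruitment as key processes. It sizes the later trial at 262 pairs, with 20% dropout as one of the inputs.

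The analysis is in Section III, Additional analysis for Aims 2-3. For dropout: "we will calculate descriptive statistics of the proportion of older adults with symptoms of SCD/MCI who choose to discontinue participation". Session completion enters there through its predictors: "as well as baseline predictors of dropout and session completion". The paragraph then says that "results will not include statistical inference", and a parenthesis explains inference as p-values. No confidence interval, precision target or retention criterion appears anywhere in the document. Recruitment is treated differently: fewer than 35 pairs in 6 months is judged against a Poisson distribution at P<.10.

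On outcomes, the sample size section says "The current trial is not intended to estimate those effect sizes". The analysis section calls the PWB comparison purely exploratory, to be used for generating hypotheses and ways of modifying the intervention. It then specifies that change scores are computed and "differences across randomization groups will be compared using the Wilcoxon rank sum test". It also mentions a comparison controlling for baseline differences, with no model named, and graphs of pre-post change. None of these comes with a stated effect estimate or interval.

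**The concern.** A pilot of 44 people gives an imprecise dropout proportion. Since that proportion bears directly on the 20% assumed for the later trial, its imprecision is part of the result. Without an interval, an observed value near 20% could be taken as confirming the assumption when it is also compatible with values that would change the later trial's size materially.

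The change-score comparison has a related gap. A rank sum test on its own yields a p-value. It does not say how large the difference is or which differences remain plausible, and an analysis meant to generate hypotheses needs that information most. In a sample this small a non-significant result is likely even if the later trial's assumed effect is real, and the p-value alone does not show this.

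**Working it through.** **Inputs from Section III.** Pilot: 44 older adults randomised 1:1, so 22 per arm, with 44 pairs recruited in 6 months. Later trial: d=0.45, power 0.90, alpha 0.05, 20% dropout, 262 pairs over 36 months. Sidedness is not stated; I take two-sided because it reproduces the plan's figure.

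**The plan's own figures.**
- Normal approximation: n per arm = 2(1.960+1.282)²/0.45² = 103.8, so 104 per arm and 208 in total; 208/0.80 = 260.
- t-test version: 104.75 per arm; 2×104.75/0.80 = 261.9, which matches 262. One-sided alpha gives 85 per arm (about 213 in total) and does not match.
- Recruitment rule: expected count = 262×6/36 = 43.67. Poisson P(X≤34) = 0.079 and P(X≤35) = 0.105, so fewer than 35 at P<.10 is correct.

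**Precision of dropout.** The counts are illustrations near 20%. The exact (Clopper-Pearson) 95% limits are the 0.025 quantile of Beta(x, n−x+1) and the 0.975 quantile of Beta(x+1, n−x).
- 9/44 (20.5%): 9.8% to 35.3%.
- 4/22 (18.2%, intervention arm only): 5.2% to 40.3%.

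**Effect on the later trial.** Assume that leaving the program means a missing outcome. The plan's evaluable number is 262×0.80 = 209.6.
- At 9.8% dropout: 209.6/(1−0.098) ≈ 232 pairs.
- At 35.3% dropout: 209.6/(1−0.353) ≈ 324 pairs.
- If 262 were kept, 35% dropout leaves 262×0.65 = 170 evaluable and t-test power of 0.83 instead of 0.90. At 20% dropout the same calculation returns 0.90.

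**The Wilcoxon test in the pilot.** Assume normal change scores with equal SDs, and a shift of 0.45 in units of the SD of change. The document gives no SD of change. If 20% of outcomes were missing, 44×0.80 = 35.2 would remain, or 17-18 per arm. Power is by simulation at two-sided 0.05. The half-width of a 95% interval for the difference, in SD units, is t(0.975, 2n−2)×√(2/n).

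| n per arm | Wilcoxon power at d=0.45 | 95% half-width |
|---|---|---|
| 22 | about 0.30 | 2.018×0.302 = 0.61 SD |
| 18 | 0.24-0.25 | 2.032×0.333 = 0.68 SD |
| 17 | 0.23 | 2.037×0.343 = 0.70 SD |

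A simulated Hodges-Lehmann interval had a mean full width of 1.26 SD at 22 per arm and 1.41 SD at 18. Its half-widths of 0.63 and 0.70 SD are close to the table.

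**The case against.** The strongest reply is that the plan is a reasonable pilot plan and allows everything asked for here. Several parts of that reply stand.

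- A reader might infer that the plan rules out intervals for dropout. It does not: the parenthesis limits the exclusion to p-values, and leaving those out is good practice for feasibility measures. The text is silent on intervals.
- A reader might infer that the plan has its priorities reversed, denying inference to feasibility and granting it to efficacy. That fails too. Recruitment, the outcome that sizes the pilot, has a probability rule and monthly review. The gap concerns retention and session completion.
- A reader might see a contradiction between excluding inference and running a Wilcoxon test. The exclusion follows the enrolment and dropout descriptives; the test belongs to the separate Aim 3 comparison.
- The plan does not say that it cannot estimate effects. It says the trial is not intended to, which leaves room for an exploratory look.
- Low power is no defect in a comparison labelled purely exploratory. No significance threshold or decision rule is attached to it, so the documents do not support a claim that a non-significant result will drive changes to the intervention.
- Dropouts who complete outcome surveys stay in the outcome analyses, so the numbers analysed may be nearer 22 per arm than 17-18.

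The reply does not remove the gap. Permission to report an interval is not a plan to report one. The exploratory label, the unspecified adjusted comparison and the graphs do not commit the study to an effect estimate with its precision. The Poisson rule shows that the investigators already quantify uncertainty for one feasibility measure; retention is named in the same goal.

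**Conclusion.** The point holds as a gap in planned precision that should be corrected. The plan's sample size and recruitment figures reproduce and are not in question.

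An observed dropout near 20% in 44 people would leave roughly 10% to 35% plausible. This corresponds to about 232 to 324 pairs around the planned 262, so the error could run in either direction. That range depends on the illustrative count of 9/44 and on treating program dropout as missing outcome data; with surveys obtained from people who stop, the effect on sample size would be smaller.

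For change scores, about 70% of pilots with complete follow-up would be non-significant under the later trial's assumed effect (1−0.30), and 75% to 77% with 17-18 per arm. These figures rest on normality and on applying d to the SD of change. They show why a p-value alone is uninformative here. They do not show that the comparison should be dropped or the pilot enlarged.

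**What to change.** In Additional analysis for Aims 2-3, keep the exclusion of p-values for dropout and session completion, and add wording such as: *The proportion who discontinue and the proportion who complete the planned sessions will each be reported with an exact 95% confidence interval. Observed dropout will be read against the 20% planning value using that interval.* The session-completion proportion is new, since the plan now names completion through its predictors, the completer definition and missed-session correlations. Its definition and denominator should be stated there. Leave the Poisson recruitment rule unchanged; the new sentence should not extend to recruitment.

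For PWB and the other change scores, make the between-group difference with a 95% confidence interval the main exploratory result, for example the Hodges-Lehmann shift, which pairs naturally with the Wilcoxon test, in place of a Wilcoxon p-value alone. State that statistical significance will not be used to decide on modifying the intervention.

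The cost is SAP wording and a few lines of code, with no new data. The results will look less certain.

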Online sessions. We will use a standard videoconferencing platform (e.g., "BlueJeans") or the SPEAK! platform for the study. While specially-customized videoconferencing software may be useful, we believe that at this stage of the research it would be wiser to invest resources in first understanding the types of customization that would be beneficial. Both older adults with symptoms of SCD/MCI and ELLs will be sent reminders prior to each session via a telephone call, email, or text message according to their preference. Videoconferences will be facilitated by study staff who will introduce each session, assist with technical issues, and ensure that both parties have their materials and are comfortable. Older adults and learners will be provided with a suggested session outline. More detailed information will be provided in a variety of formats including a comprehensive manual, flashcards, and lists of common phrases to ensure that conversations do not stall. Our expectation based on initial experience with older adults who do not have symptoms of SCD/MCI is that pairs will meet online for a one-hour session once a week for a total of 8 weeks. Meta-analyses of factors determining the impact of volunteering or psychological interventions indicate that effects are not sensitive to the number or duration of sessions. However, we will specifically inquire about the length and frequency of sessions during follow-up surveys and qualitative interviews with participants for Aim 1. Based on that feedback and

more detailed input from experts in gerontologic mental health, the frequency and duration of sessions may be modified.

While we fully expect that conversations will be a positive and productive experience for the older adult with symptoms of SCD/MCI and ELL, training materials will include a discussion of topics that both parties should avoid. These will include financial problems, medical problems, or potentially contentious issues such as political or religious differences. We will make special emphasis regarding types of comments that would be considered inappropriate, even as “jokes.” We will inquire about questions and comments that would be considered too sensitive during the Aim 1 development interviews. Pairs will be instructed regarding the types of information that they should never share, such as financial data, and we will emphasize the importance of being available at scheduled times and communicating in advance if availability changes.

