Older adults with symptoms of SCD/MCI will have the opportunity to use videoconferencing software that may be new to them – a skill they can use for communicating with family and other social network members at a distance. Our hypothesis is that sessions with ELLs will increase older adults' sense of social engagement and purpose (which may improve their mood); and that the conversations may improve aspects of their cognitive functioning. ELLs will have the opportunity to build skills and confidence related to English fluency, and this may be useful as they seek jobs and training opportunities. ELLs who complete 6 out of 8 sessions will receive a certificate acknowledging their participation in the program. Such certificates are highly valued among language learners and can be useful to support job applications for positions that require communication with English-speakers (e.g., work in hotels or restaurants).

4. Importance of Knowledge to be Gained

This research study has an excellent risk/benefit ratio. While risks to participants are minimal, the potential benefit is great. If the results of the proposed trial are positive, the study will identify a scalable and cost-effective strategy for increasing social engagement among older adults with symptoms of SCD/MCI and consequently improving their mental health and lowering their risk for cognitive decline.

Data and Safety Monitoring

The research team is very experienced in maintaining the security of research data. Participants will be assigned a unique study identification number that will serve as their primary identifier for all analytic files. We will create a secure electronic tracking file that maps the participant's identifying information to the study ID number. A hard copy of the cross-walk file will be maintained in a locked file cabinet separately from other study-related documents, and an electronic version of the cross-walk will be maintained in a secure directory accessible only to the PI and authorized staff members. Identifiers of potential recruits and study participants will be maintained throughout the data collection phase to allow for follow-up contacts and to ensure that study refusals/drop-outs are not inadvertently re-contacted. Following the completion of data collection and once datasets have been cleaned and built, the linkage code will be securely overwritten using a standard protocol for removal/destruction of sensitive material.

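### The completer analysis applies its attendance cut to the intervention arm only, so selected attenders are set against unselected controls, or against none

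*Combined protocol and SAP*

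**What the plan says.** All references are to the combined protocol and SAP.

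- **Outcome comparison (section III, Additional analysis for Aims 2-3).** "In a purely exploratory mode, we will examine differences in outcomes between intervention and control groups, controlling for any baseline differences in group characteristics". Change scores are compared between the randomised groups with a Wilcoxon rank sum test. Older adults who drop out, or who "complete less than the expected number of sessions but complete outcome surveys will be included in outcome analyses".
- **Completer analysis (same paragraph, next sentence).** The plan adds completer "analyses including only intervention-group older adults who complete 8 out of the 12 planned sessions", with a parenthesis allowing the equivalent out of 8. No rule is given for the waitlist group and no comparator is stated.
- **Attendance (same section).** The plan will describe discontinuation "as well as baseline predictors of dropout and session completion, with a particular emphasis on baseline measures of cognitive functioning", and also PWB and depressive symptoms.
- **Waitlist arm (section III, Aim 2-3 waitlist controlled trial).** "Older adults with symptoms of SCD/MCI assigned to the waitlist control will be matched with an ELL after completing their 8-week follow-up survey", and then complete the same 8-week programme.
- **Timing (section II, Sequence of the investigation).** Data collection ends in month 20, waitlist participants finish the programme in month 23, and analysis occupies months 23-24.
- **Sessions (section II, Online sessions).** The expectation is that "pairs will meet online for a one-hour session once a week for a total of 8 weeks". Staff introduce each session.

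**The concern.** Randomisation makes the two arms comparable as whole groups. Once low attenders are removed from one arm only, the other arm still contains their counterparts. If the tendency to attend is related to how people would have changed without the programme, the contrast is non-zero even when the programme does nothing. Reading the sentence as a pre-post analysis of completers does not help, because there is then no control for time, retesting or selection.

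The characteristics the plan will examine as predictors of session completion (cognition, PWB, depressive symptoms) are also measured as outcomes, so such a relation is plausible. The sample-size paragraph in section III lists dose-response among the matters a pilot should assess, and this is the only planned outcome analysis that depends on attendance. A spurious completer difference could be taken as a sign that more sessions help.

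**Working it through.** **Inputs from the documents.** 44 older adults randomised 1:1, so 22 per arm. The later trial is sized for d = 0.45 with 0.90 power, a 0.05 level and 20% dropout, giving 262 pairs. No completion proportion, sample size or power is given for the completer analysis.

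**Check of the benchmark.** 2 × (1.960 + 1.282)² / 0.45² = 103.8, so 104 per arm and 208 in all; 208 / 0.80 = 260. The t-test version gives 105 per arm, and 210 / 0.80 = 262.5, rounded up to 263. The stated 262 is consistent with a two-sided test, so d = 0.45 is a fair yardstick.

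**Assumed inputs.** Completion proportion p = 0.5 to 0.8. Correlation r between the tendency to complete and untreated change = 0.2 to 0.5, taken as positive.

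**Bias of the one-sided contrast, null programme.** With a normal attendance tendency and change scaled to SD 1, bias = r × φ(z) / p, where z = Φ⁻¹(1 − p).

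| p | φ(z)/p | r = 0.2 | r = 0.3 | r = 0.5 |
|---|---|---|---|---|
| 0.50 | 0.798 | 0.160 | 0.239 | 0.399 |
| 0.65 | 0.570 | 0.114 | 0.171 | 0.285 |
| 0.80 | 0.350 | 0.070 | 0.105 | 0.175 |

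A negative r gives the same sizes with the opposite sign.

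**Against sampling error.** At p = 0.65 there are 14.3 expected completers. SE = √(1/14.3 + 1/22) = 0.34 SD, so a bias of 0.17 is about half a standard error. In simulation with 22 per arm and no effect, the Wilcoxon test at nominal 0.05 rejected in 6.7% of runs (p = 0.7, r = 0.3), 5.8% (0.8, 0.3), 11.2% (0.7, 0.5) and 7.5% (0.8, 0.5).

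**Restricting both arms, using later waitlist attendance.** The bias becomes (r − r′) × φ(z) / p, where r′ is the correlation between later attendance tendency and change over the waiting period. Take p = 0.7 (φ(z)/p = 0.497) and r = 0.3, for which the one-sided bias is 0.15.

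- Later attendance identical to immediate attendance: r′ = 0.3, bias 0.
- The two tendencies correlate 0.7: r′ = 0.21, bias 0.09 × 0.497 = 0.04. At correlation 0.5 it is 0.07; at 0 it is 0.15, with no gain.
- Later attendance also depends on the 8-week change, with coefficient g: r′ = (r + g) / √(1 + g² + 2gr). For g = −0.3, r′ = 0 and the bias is +0.15. For g = +0.3, r′ = 0.6 / √1.27 = 0.532 and the bias is −0.12.

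At p = 0.65 the SE rises from 0.34 to √(2/14.3) = 0.37, about 10%.

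**Complier-average estimate.** This is the all-randomised difference divided by p. Under a null programme with complete outcome data it is centred on zero. At p = 0.65 its SE is about √(2/22) / 0.65 = 0.302 / 0.65 = 0.46. It overstates the completer effect if partial attenders benefit. As an illustration with assumed figures, let benefit be linear in sessions, with completers averaging 7.5, others 2.5, and 65% completing. The overall effect is 0.65 × 7.5 + 0.35 × 2.5 = 5.75 units, and 5.75 / 0.65 = 8.85 against a true 7.5, which is 18% too high.

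**The cut itself.** 8/12 of 8 sessions is 5.33, which is not a whole number.

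**The case against.** The case for leaving the plan alone is substantial. The analysis is an addition, everything around it is labelled exploratory, partial attenders with outcome surveys stay in the outcome analyses, and the plan disclaims any intention to estimate effect sizes. No decision rule uses the completer result. All of this stands, and it keeps the importance low. It does not remove the selection.

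The plan also intends to control for baseline group differences. It does not say that this extends to the completer analysis. Adjustment would remove only what measured baseline variables explain, though the bias figures above make no allowance for it.

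The magnitude rests on assumptions. The predictors named are baseline values, whereas r concerns untreated change. If completers start with higher PWB, regression to the mean could make r negative. The SD of change may also differ from the SD behind d = 0.45: if that d uses the score SD and the pre-post correlation is 0.7, 0.17 becomes 0.17 × √(2 × 0.3) = 0.13. These points stand.

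Several stronger readings are tempting, and the documents do not support them.

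- A reader might infer that waitlist attendance supplies like-for-like controls at no cost. It occurs after an 8-week wait and after the control outcome is measured, so that outcome may influence it. Waitlist sessions also run to month 23, although data collection is scheduled to end in month 20, and precision is lost.
- A reader might infer that the plan will decide how to modify the programme from the completer result. The text says that exploratory PWB differences will generate hypotheses and strategies, and it says so before the completer analysis is introduced.
- A reader might infer that the plan expects attendance to depend on the outcomes. It proposes only to describe baseline predictors, without p-values.

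**Conclusion.** The point holds, with low importance. The session cut is stated for one randomised arm, so any contrast with the waitlist arm is a non-randomised comparison, and a pre-post reading has no control. That the comparator is the whole control group is the natural reading, because the sentence follows directly on the intervention-control comparison, but it remains an inference.

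Under a null programme the spurious difference is about 0.07-0.40 SD of change, and 0.17 at 65% completion and a correlation of 0.3. This assumes 50-80% completion, a positive correlation of 0.2-0.5 and no baseline adjustment. The documents establish neither the inputs nor the direction, so it cannot be said that the analysis favours the programme. Restricting both arms to completers is not a clean cure: it removes the bias only if later attendance stands in for immediate attendance and is unaffected by the 8-week outcome. Otherwise the bias can persist or reverse.

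**What to change.** In section III, Additional analysis for Aims 2-3:

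1. Reconcile the 8-of-12 cut with the 8-session design and state it as a whole number of sessions. The learner certificate rule in section IV ("ELLs who complete 6 out of 8 sessions will receive a certificate acknowledging their participation in the program") is a separate threshold and does not settle this.
2. State that the comparison of all randomised participants with outcome data is the main one. Name the comparator of the one-sided completer contrast and label that contrast non-randomised.
3. For the dose-related question, report the complier-average estimate: the all-randomised difference divided by the intervention-arm completion proportion. State that it assumes no benefit from attendance below the cut, and that it overstates the completer effect if partial attenders benefit.
4. Keep waitlist session counts to month 23. As a sensitivity analysis only, compare intervention completers with waitlist participants who later reach the same cut, using the latter's 8-week outcome from before their programme. State the assumption that neither the wait nor the 8-week outcome affects who completes.

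The cost is a few sentences of text, a little more analysis in months 23-24, and attendance counts kept beyond the scheduled end of data collection; no new survey is needed. At 65% completion the sensitivity analysis has about a third fewer controls and an SE about 10% larger. The complier-average estimate is less precise still (about 0.46 SD).
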